# **Additional Categories**

- 7. Have measurable disease per RECIST 1.1 as assessed by the local site investigator/radiology. Lesions situated in a previously irradiated area are considered measurable if progression has been demonstrated in such lesions. For Part 1 only: Cutaneous lesions can be considered in addition to imaging, but measurable disease should be defined by radiologic assessment.
- 8. Have an evaluable archival tumor sample to submit for analysis. Formalin-fixed, paraffin embedded (FFPE) tissue blocks are preferred to slides.
  - Note: If submitting unstained cut slides, newly cut slides should be submitted to the testing laboratory within 14 days from the date slides are cut. Details pertaining to tumor tissue submission can be found in the Procedures Manual.
- 9. Have adequate organ function as defined in the following table (Table 2). Specimens must be collected within 7 days prior to the start of study intervention.

Table 2 Adequate Organ Function Laboratory Values

System	Laboratory Value					
Hematological						
Absolute neutrophil count (ANC)	≥1500/µL					
Platelets	≥100 000/µL					
Hemoglobin	≥9.0 g/dL or ≥5.6 mmol/L¹					
Renal						
Creatinine OR Measured or calculated  creatinine clearance (GFR can also be used in place of creatinine or CrCl)	≤1.5 × ULN OR ≥30 mL/min for participant with creatinine levels >1.5 × institutional ULN					
Hepatic						
Total bilirubin	≤1.5 ×ULN OR direct bilirubin ≤ULN for participants with total bilirubin levels >1.5 × ULN					
AST (SGOT) and ALT (SGPT)	≤2.5 × ULN (≤5 × ULN for participants with liver metastases)					
Coagulation						
International normalized ratio (INR) OR prothrombin time (PT) Activated partial thromboplastin time (aPTT)	≤1.5 × ULN unless participant is receiving anticoagulant therapy as long as PT or PTT is within the rapeutic range of intended use of anticoagulants					

ALT (SGPT)=alanine aminotransferase (serum glutamic pyruvic transaminase); AST (SGOT)=aspartate aminotransferase (serum glutamic oxaloacetic transaminase); GFR=glomerular filtration rate; ULN=upper limit of normal.

Criteria must be met without erythropoietin dependency and without packed red blood cell (pRBC) transfusion within last 2 weeks.

Creatinine clearance (CrCl) should be calculated per institutional standard.

Note: This table includes eligibility-defining laboratory value requirements for treatment; laboratory value requirements should be adapted according to local regulations and guidelines for the administration of specific chemotherapies.

10. Have a performance status of 0 or 1 on the Eastern Cooperative Oncology Group (ECOG) Performance Scale.

In order to be eligible to crossover from Arm A into Arm B in Part 1 of this trial, the participant must meet the following criteria:

11. Have radiographic disease progression as defined by RECIST v1.1 on Arm A mRNA-5671/V941 monotherapy and have Sponsor approval for crossover.

#### 5.2 Exclusion Criteria

Participants are excluded from the study if any of the following criteria apply:

#### **Medical Conditions**

1. A WOCBP who has a positive urine pregnancy test within 72 hours prior to randomization or treatment allocation (see Appendix 5). If the urine test is positive or cannot be confirmed as negative, a serum pregnancy test will be required.

Note: In the event that 72 hours have elapsed between the screening pregnancy test and the first dose of study treatment, another pregnancy test (urine or serum) must be performed and must be negative in order for participant to start receiving study medication.

- 2. Has an active infection requiring therapy.
- 3. Has a history of interstitial lung disease.
- 4. Has an active autoimmune disease that has required systemic treatment in the past 2 years (ie, with use of disease modifying agents, corticosteroids, or immunosuppressive drugs) except vitiligo or resolved childhood asthma/atopy. Replacement therapy, such as thyroxine, insulin, or physiologic corticosteroid replacement therapy for adrenal or pituitary insufficiency, is not considered a form of systemic treatment and is allowed. Use of nonsystemic steroids is permitted.
- 5. Has conditions, therapy, or laboratory abnormality that might confound the results of the study, interfere with the participant's participation for the full duration of the study, make administration of the study drugs hazardous, or make it difficult to monitor adverse effects such that it is not in the best interest of the participant to participate, in the opinion of the treating investigator.
- 6. Has not fully recovered from any effects of major surgery or has evidence of detectable infection. Surgeries that required general anesthesia must be completed at least 2 weeks before first study treatment administration. Surgery requiring regional/epidural anesthesia must be completed at least 72 hours before first study treatment administration and participants should be recovered.

# Prior/Concomitant Therapy

7. Has had chemotherapy, definitive radiation, or biological cancer therapy within 4 weeks (2 weeks for palliative radiation) prior to the first dose of study therapy, non-cytotoxic small molecule therapeutics within 5 half-lives (or 2 weeks, whichever is longer) prior to the first dose of study treatment, or has not recovered to CTCAE Grade 1 or better from any adverse events that were due to cancer therapeutics administered more than 4 weeks earlier (this includes participants with previous immunomodulatory therapy with residual immune-related adverse events). Participants receiving ongoing replacement hormone

V941-001-08 FINAL PROTOCOL 24-MAR-2022

- therapy for endocrine immune-related adverse events will not be excluded from participation in this study.
- 8. Has received a live-virus vaccine within 30 days of planned treatment start. Seasonal flu vaccines that do not contain live virus are permitted. Refer to Section 6.5 for information on COVID-19 vaccines.
- 9. Has received hematopoietic colony-stimulating growth factors (eg, granulocyte-colony stimulating factor, erythropoietin, granulocyte-macrophage-colony stimulating factor, macrophage-colony stimulating factor) within 2 weeks prior to the first dose of study intervention.
- 10. Discontinued from therapy with an anti-PD-1, anti-PD-L1, or anti-PD-L2 agent or with an agent directed to another stimulatory or co-inhibitory T-cell receptor (TCR; eg, CTLA-4, OX 40, and CD137) due to a Grade 3 or higher immune-related adverse event (irAE).

# **Prior/Concurrent Clinical Study Experience**

11. Is currently participating in or has participated in a study of an investigational agent or has used an investigational device within 28 days prior to the first dose of study intervention.

Note: Participants who have entered the follow-up phase of an investigational study may participate as long as it has been 4 weeks after the last dose of the previous investigational agent.

#### **Diagnostic Assessments**

- 12. Has a diagnosis of immunodeficiency or is receiving chronic systemic steroid therapy (in dosing exceeding 10 mg daily of prednisone equivalent) or any other form of immunosuppressive therapy within 7 days prior the first dose of study drug.
- 13. Has a known additional malignancy that is progressing or has required active treatment within the past 2 years.
  - Note: Participants with basal cell carcinoma of the skin, squamous cell carcinoma of the skin, or carcinoma in situ (eg, breast carcinoma, cervical cancer in situ) that have undergone potentially curative therapy are not excluded.
- 14. Has known active CNS metastases and/or carcinomatous meningitis. Participants with previously treated brain metastases may participate provided they are radiologically stable, (ie, without evidence of progression) for at least 4 weeks by repeat imaging (note that the repeat imaging should be performed during study screening), clinically stable and without requirement of steroid treatment for at least 14 days prior to first dose of study intervention.

- 15. Has severe hypersensitivity (≥Grade 3) to pembrolizumab and/or any of its excipients.
- 16. Has a history of (non-infectious) pneumonitis that required steroids or has current pneumonitis.
- 17. Has a known history of Hepatitis B (defined as Hepatitis B surface antigen [HBsAg] reactive) or known active Hepatitis C virus (defined as HCV RNA [qualitative] is detected) infection.

Note: No testing for Hepatitis B and Hepatitis C is required unless mandated by local health authority.

18. Has a known history of HIV.

Note: No testing for HIV is required unless mandated by local health authority.

19. Has a known psychiatric or substance abuse disorder that would interfere with cooperating with the requirements of the study.

#### Other Exclusions

- 20. Is pregnant or breastfeeding or expecting to conceive or father children within the projected duration of the study, starting with the screening visit through 120 days after the last dose of study intervention.
- 21. Has had an allogenic tissue/solid organ transplant.

#### 5.3 Lifestyle Considerations

# 5.3.1 Meals and Dietary Restrictions

Participants should maintain a normal diet unless modifications are required to manage an AE such as diarrhea, nausea, or vomiting.

# 5.3.2 Contraception

Pembrolizumab and/or mRNA-5671/V941 may have adverse effects on a fetus in utero. Refer to Appendix 5 for approved methods of contraception.

Participants should be informed that taking the study medication may involve unknown risks to the fetus (unborn baby) if pregnancy were to occur during the study. In order to participate in the study, participants of childbearing potential must adhere to the contraception requirement (Appendix 5) from the day of study medication initiation (or 14 days prior to the initiation of study medication for oral contraception) throughout the study period up to 120 days after the last dose of study medication. If there is any question that a participant of childbearing potential will not reliably comply with the requirements for contraception, that participant should not be entered into the study.

#### 5.3.3 **Pregnancy**

If a participant inadvertently becomes pregnant while on treatment, the participant will be immediately discontinued from study intervention. The site will contact the participant at least monthly and document the participant's status until the pregnancy has been completed or terminated. The outcome of the pregnancy will be reported to the Sponsor without delay and within 24 hours if the outcome is a serious adverse experience (eg, death, abortion, congenital anomaly, or other disabling or life-threatening complication to the mother or newborn). The study Investigator will make every effort to obtain permission to follow the outcome of the pregnancy and report the condition of the fetus or newborn to the Sponsor. If a male participant impregnates his female partner, the study personnel at the site must be informed immediately and the pregnancy must be reported to the Sponsor and followed as described in Section 8.4.

#### 5.3.4 Use in Nursing Women

It is unknown whether pembrolizumab is excreted in human milk. Since many drugs are excreted in human milk, and because of the potential for serious adverse reactions in the nursing infant, participants who are breastfeeding are not eligible for enrollment.

#### 5.4 **Screen Failures**

V941-001-08 FINAL PROTOCOL

Screen failures are defined as participants who consent to participate in the clinical study, but are not subsequently entered in the study. A minimal set of screen failure information is required to ensure transparent reporting of screen failure participants to meet the Consolidated Standards of Reporting Trials (CONSORT) publishing requirements and to respond to queries from regulatory authorities. Minimal information includes demography, screen failure details, eligibility criteria, and any AEs or SAEs meeting reporting requirements as outlined in the data entry guidelines.

#### 5.5 **Participant Replacement Strategy**

In order to adequately evaluate the safety of the doses administered in this study, all participants enrolled must meet the criteria for evaluability for Cycle 1. Participants are considered nonevaluable and will be replaced if:

- They are allocated but not treated.
- They discontinue from the trial prior to completing all the safety evaluations for reasons other than treatment-related adverse events during Cycle 1 in the dose finding phase of the study (Part 1).
- They receive less than 100% of the total mRNA-5671/V941 or less than 90% of the total pembrolizumab infusion in Cycle 1 (eg, if the infusion had to be discontinued due to an infusion reaction) and did not experience a DLT.

Participants who are not evaluable will be replaced unless accrual to the cohort has stopped. Nonevaluable participants will not be counted toward the total number of participants in the cohort for DLT evaluation.

If a participant experiences a DLT in Cycle 1, trial treatment may be discontinued following discussion between the Sponsor and investigator. However, if the participant is deriving clinical benefit from the trial treatment, the participant may be allowed to continue after discussion between the Sponsor and the investigator.

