### **6.6.2** Definition of Dose-limiting Toxicity

All toxicities will be graded using NCI-CTCAE Version 4.0 based on the investigator assessment.

The DLT window of observation will be 21 days from the first dose of study treatment (Cycle 1). Participants will be monitored for DLTs during treatment with mRNA-5671/V941 as a monotherapy as well as in when mRNA-5671/V941 is administered in combination with pembrolizumab.

For dose-escalation decisions, an evaluable participant is defined as a participant who meets one of the following criteria:

• Receives any amount of an mRNA-5671/V941 dose alone or in combination with a pembrolizumab dose and experiences a DLT during Cycle 1.

24-MAR-2022

V941-001-08 FINAL PROTOCOL

Receives 100% of an mRNA-5671/V941 dose in Arm A, Cycle 1 or 100% of an mRNA-5671/V941 dose and/or ≥ 90 % of a pembrolizumab dose in Arm B, Cycle 1, is followed up for ≥ 21 days after the first dose of study treatment, and does not experience a DLT.

Participants who are not considered to be evaluable may be replaced (Section 5.5).

The occurrence of any of the following toxicities will be considered a DLT if judged by the investigator to be possibly related to administration of either mRNA-5671/V941 monotherapy or mRNA-5671/V941 in combination with pembrolizumab (ie, the toxicity is not attributable to the disease or disease-related processes under investigation or other causes):

- 1. Grade 4 nonhematologic toxicity (ie. Not a laboratory finding).
- 2. Grade 4 hematologic toxicity lasting  $\geq 7$  days, except thrombocytopenia:
- 3. Grade 4 thrombocytopenia of any duration
- 4. Grade 3 thrombocytopenia associated with clinically significant bleeding
- 5. Any nonhematologic AE ≥ Grade 3 in severity should be considered a DLT, with the following exceptions: Grade 3 fatigue lasting ≤ 3 days; Grade 3 diarrhea, nausea, or vomiting that does not require anti-emetics or anti-diarrheals per standard of care; Grade 3 rash that does not require corticosteroids or anti-inflammatory agents per standard of care.
- 6. Any Grade 3 or Grade 4 nonhematologic laboratory value that meets one of the following criteria:
  - Clinically significant medical intervention is required to treat the participant.
  - The abnormality leads to hospitalization.
  - The abnormality persists for >1 week.
  - The abnormality results in a drug-induced liver injury.

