## 9.5 Analysis Populations

## 9.5.1 Safety Analysis Populations

The All-Subjects-as-Treated (AsaT) population will be used for the analysis of safety data in this study. The AsaT population consists of all participants who received at least 1 dose of study treatment.

The DLT evaluable population includes AsaT participants that meet the criteria for DLT evaluability (eg, finished Cycle 1 without a DLT or experienced a DLT in Cycle 1). See Section 6.6.2 for details.

At least 1 laboratory or vital sign measurement obtained subsequent to at least 1 dose of study treatment is required for inclusion in the analysis of each specific parameter. To assess change from baseline, a baseline measurement is also required.

Data from participants who crossover from monotherapy to the combination therapy will be presented separately.

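### Section 5.5's early-exit rule lacks the DLT exception and contradicts Sections 6.6.2 and 9.5.1 on whether an observed Cycle 1 DLT is counted (minor)

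*Combined protocol and SAP*

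**What the plan says.** Section 5.5 gives three grounds on which a participant is nonevaluable and is to be replaced:

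1. Allocated but never treated.
2. Early exit in Part 1: "They discontinue from the trial prior to completing all the safety evaluations for reasons other than treatment-related adverse events during Cycle 1".
3. Incomplete Cycle 1 dosing, which applies only if the participant received too little "and did not experience a DLT".

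The section then states the consequence: "Nonevaluable participants will not be counted toward the total number of participants in the cohort for DLT evaluation".

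Section 6.6.2 defines evaluability separately and says what the definition is for: "For dose-escalation decisions, an evaluable participant is defined as a participant who meets one of the following criteria". The first of its two criteria is "Receives any amount of an mRNA-5671/V941 dose alone or in combination with a pembrolizumab dose and experiences a DLT during Cycle 1". It sets no condition on completing the cycle, on follow-up or on the reason for leaving. The section ends by pointing back: "Participants who are not considered to be evaluable may be replaced (Section 5.5").

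SAP Section 9.5.1 describes the DLT-evaluable population by example, "finished Cycle 1 without a DLT or experienced a DLT in Cycle 1", and refers to 6.6.2 for detail.

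**The concern.** The second ground in 5.5 turns on why the participant left, not on whether a DLT had already occurred. A participant can have a DLT and then leave for a different recorded reason. Under 5.5 that person is replaced and the event goes from the DLT count. Under 6.6.2 and 9.5.1 the same person is evaluable with a DLT. The DLT exception in the third ground suggests that its absence from the second is an oversight.

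DLT incidence is a primary endpoint and the input to the mTPI rule in Table 1. Cohorts may start with three participants, so one record can settle a dose decision. If a site or study team worked from 5.5 alone, a DLT that had been seen would be dropped and its place refilled. The count behind the dose decision could then differ from the SAP's DLT estimate.

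**Working it through.** **Step 1. Apply each section to the same records.**

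| Cycle 1 record | 5.5, literal | 6.6.2 and 9.5.1 |
|---|---|---|
| Related Grade 4 nonhematologic event on Day 5, consent withdrawn on Day 9 | Nonevaluable, replaced, not counted | Evaluable, with a DLT |
| No DLT, consent withdrawn on Day 9 | Nonevaluable | Nonevaluable (21 days of follow-up not reached) |
| Leaves because of a treatment-related event | Exempt from the second ground | Evaluable, with a DLT (criterion 9 in 6.6.2, if the toxicity stops treatment) |

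Only the first row conflicts.

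**Step 2. Reproduce Table 1.** Inputs from Section 4.3.4 are a 30% target, a Beta(1,1) prior and ε1 = ε2 = 0.03. The documents do not state the DU cut-off; I assume DU when P(rate > 0.30) exceeds 0.95. With x DLTs in n, the posterior is Beta(1+x, 1+n−x). The unit probability masses are:

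- E: P(rate < 0.27)/0.27
- S: P(0.27 < rate < 0.33)/0.06
- D: P(rate > 0.33)/0.67

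The largest mass decides unless DU applies. For 2/3 the masses are E 0.23, S 0.76 and D 1.33, and P(rate > 0.30) = 0.916, giving D. All five worked examples in 4.3.4 reproduce (0/3 E, 1/3 S, 2/3 D, 3/3 DU, 4/6 DU), and the grid agrees with the legible rows of Table 1.

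**Step 3. Remove one DLT.** Suppose the replacement has no DLT, so the table is read at (x−1, n) instead of (x, n). For n = 3 to 14 the number of cells with x ≥ 1 is 3 + 4 + … + 14 = 102. The decision changes in 31, each time toward less caution:

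| Change | Cells | Examples |
|---|---|---|
| S to E | 12 | 1/3, 2/6, 3/14 |
| D to S | 7 | 2/3, 5/10, 7/14 |
| DU to D | 7 | 3/3, 8/14 |
| DU to S | 5 | 3/4, 4/6 |

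Section 4.3.4 says that E at the highest dose means staying, so the 12 S-to-E changes have no effect there. That leaves 31 − 12 = 19. Many cells do not move; 3/6 and 6/14 remain S.

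**Step 4. Effect on the DLT rate.** Let p be the true rate, and w0 and w1 the probabilities of leaving in Cycle 1 for other reasons without and with a DLT. Neither is in the documents, so the values below are assumptions.

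- Expected rate under 6.6.2: p / [p + (1−p)(1−w0)]
- Expected rate under literal 5.5: p(1−w1) / [p(1−w1) + (1−p)(1−w0)]

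With p = 0.40 and w0 = 0.10:

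| Rule | w1 | Expected rate | P(D or DU) at n = 14 |
|---|---|---|---|
| 6.6.2 | any | 0.40/0.94 = 42.6% | 0.38 |
| 5.5 | 0.10 | 0.36/0.90 = 40.0% | 0.31 |
| 5.5 | 0.20 | 0.32/0.86 = 37.2% | 0.23 |
| 5.5 | 0.30 | 0.28/0.82 = 34.1% | 0.17 |

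At the true rate of 40%, P(D or DU) is 0.31. The 5.5 rule therefore falls below the truth only when w1 exceeds w0. With w1 = w0 it is unbiased in the long run, while 6.6.2 runs slightly high.

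**Step 5. How often it could arise.** The chance of at least one dropped DLT among 14 treated is 1 − (1 − p·w1)^14. For p and w1 both between 5% and 10%, it runs from 3% to 13%. For p = 30% and w1 of 10%, 20% or 30%, it is 35%, 58% or 73%.

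**The case against.** The best reply is that the plan, read as a whole, already counts the DLT. Section 6.6.2 is the definition made for dose decisions, it sends only nonevaluable participants to 5.5, Table 1 is indexed by participants evaluable for DLT, and the SAP population refers to 6.6.2. A reader might infer from 5.5 that the trial's rule is to discard such DLTs, or that 5.5 is the text that runs the mTPI count. The documents support neither inference. This stands: the finding is a contradiction between sections.

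The situation is also rare. It needs a DLT followed within the 21-day window by exit for a different recorded reason. Progression is a weak example, because Section 7.1 keeps participants who stop treatment for confirmed progression in the study, although Section 4.1 is worded more loosely. Consent withdrawal is the clear one.

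The sponsor can add that Section 9.9 expects a tolerable profile and that Section 4.3.2 reports no DLTs in 75 patients given the related vaccine. The low end of Step 5 may then be the relevant one. The event would still appear in the adverse event analysis of all treated participants, and the dose carried forward rests on the totality of the data.

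These replies limit the size of the problem. They do not remove the conflict: no clause says which section prevails, and 5.5 makes replacement mandatory where 6.6.2 makes it optional.

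**Conclusion.** The contradiction is real and minor. For a Part 1 participant with a Cycle 1 DLT who then leaves the trial in Cycle 1 for another recorded reason, 5.5 says not to count and 6.6.2 and 9.5.1 say to count.

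If 5.5 were followed, one such record could change the dose decision in up to 31 of 102 Table 1 cells, or 19 once the S-to-E changes that do nothing at the highest dose are set aside. This assumes the 0.95 DU cut-off and a replacement without a DLT.

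A reader might infer that literal 5.5 always makes a dose look safer than it is. That does not follow. The fall from 0.38 to 0.31 in Step 4 only returns to the value at the true rate. Bias below the truth requires participants with a DLT to leave more often than those without, and the documents give no exit rates from which to judge this.

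**What to change.** End the second ground in 5.5 with the words the third already carries, "and did not experience a DLT". State that the 6.6.2 evaluable set is used both for Table 1 decisions and for the SAP DLT estimate, so that anyone with a Cycle 1 DLT is in numerator and denominator whatever the later reason for leaving. Align the mandatory and optional replacement wording of 5.5 and 6.6.2 at the same time. If dose finding is already complete, confirm that no participant with a DLT was replaced under 5.5.

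The cost is a clause and a sentence, with no added participants or procedures. The one downside is a slightly higher estimated DLT rate. With 10% of DLT-free participants leaving, a true 30% would be expected to read 0.30/(0.30 + 0.70 × 0.90) = 32.3%. Section 6.6.2 already implies this.
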